11.1. Safety assessments

Safety parameters include adverse events and haematology and blood chemistry assays. Safety evaluations will be performed as indicated in the Flowchart and will include characterization of the

frequency and severity of adverse events, complete blood cell counts with differential, serum chemistries and electrolytes, and change in weight and body surface area (BSA).

11.2.1. Adverse event – definition

- An **adverse event (AE)** is any adverse change from the patient's baseline condition, i.e. any subjective signs and symptoms, or change in a concomitant disease present at selection visit. This includes inter-current signs, symptoms, illness and significant deviations from baseline laboratory values, which may occur during the course of the clinical study, whether considered related to treatment or not.

All laboratory tests for which abnormal results are collected after study treatment initiation should be repeated until the values return to normal or to stable status. Abnormal results are defined as those falling outside the laboratory normal range that are clinically significant.

The frequency with which such checks should be made will be defined at the investigator's opinion depending on the degree of abnormality.

In all cases, the aetiology should, as much as possible, be identified and the sponsor notified.

11.2.2. Reporting of adverse events

Any adverse or intercurrent event occurring during the study period, spontaneously reported by the patient or observed by others, and considered related to the study treatment will be recorded in the source documents as well as in the electronic Case Report Form (eCRF). The records will describe the nature (diagnosis, signs and symptoms), severity, date/time of onset, date/time of end, outcome and actions taken, and relationship to study treatment (according to the investigator's opinion).

Moreover, the investigator must assess for each adverse event recorded: its seriousness (see definition of "Serious Adverse Event" in section 11.2.3), its severity (intensity) according to **NCI-CTCAE v 4.0** (https://evs.nci.nih.gov/ftp1/CTCAE/CTCAE_4.03/CTCAE_4.03_2010-06-14_QuickReference_8.5x11.pdf), its causal relationship with the study treatment or with any study-mandated procedure or activity.

The following events should be reported in the 'Adverse Events' section of the e-CRF:

- **adverse events with the maximum grade per cycle (excepted grade 1 haematological events)**, meaning that if several adverse events of the same nature occur during the same cycle, but with a different grade, only event with the highest grade must be reported. An event that covers more than one cycle is recorded once in the database.

- **all serious adverse events, of any grade**

It is recommended to confirm the causal relationship of each non-serious or serious adverse event with the investigator, before updating database.

AEs already recorded and designated as "continuing", should be reviewed at each subsequent assessment. If resolved, the details in the eCRF are completed.

If any AE changes for the worse, in frequency of attacks/symptoms or in severity, a new record of the event must be started (i.e. distinct reports are required for differing frequencies and/or severity of the same event to enable comprehensive safety reports and later analysis).

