Response rates will be estimated in each treatment group along with a 90% confidence interval. Survival rates will be estimated according to the Kaplan-Meier method. Median survival times will be presented along with a 95% confidence interval. Correlations will be evaluated with the Spearman correlation coefficient.

After amendment 5.0 in July 2018

A comparison between arms VIT vs VI will be performed to estimate the relative effect of VIT compared to VI, for all efficacy and safety endpoints. Objective response rates will be compared using Mantel-Haenszel Chi 2 test adjusted for confounding factors (histological subtype: alveolar, including pure or alveolar component vs non alveolar; and disease status at study entry: metastatic relapse/progression vs localised disease). OS and PFS curves will be compared using stratified logrank tests. Hazard ratios will be estimated using Cox models controlling for confounding factors. A future multi-arm multi-stage randomised phase II/III trial (FaR-RMS) plans comparing selected experimental arm(s) to control arm in the same setting. If the VI treatment is kept as a control arm and VIT as one of the experimental arms for the FaR-RMS trial, a joint analysis of both trials (VIT

and FaR-RMS) will be planned in order to provide efficacy results of VIT vs VI comparison (response rate, OS and PFS curves) on a larger sample of patients.

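### Protocol 11.2.2 opens by tying adverse event recording to judged relatedness, against 11.2.1 and its own reporting list; for non-serious events this could bias the VIT versus VI safety comparison

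*Protocol*

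**What the plan says.** Section 11.2.1 defines an adverse event as an unfavourable change from baseline, "which may occur during the course of the clinical study, whether considered related to treatment or not".

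Section 11.2.2 then gives instructions that do not agree with one another:

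- The opening sentence sets the recording rule. Its decisive part reads: "and considered related to the study treatment will be recorded in the source documents as well as in the electronic Case Report Form (eCRF").
- Each recorded event is to be assessed for seriousness, severity and "its causal relationship with the study treatment or with any study-mandated procedure or activity".
- The list of what goes into the adverse event section of the eCRF has two items: "adverse events with the maximum grade per cycle (excepted grade 1 haematological events") and "all serious adverse events, of any grade". Neither mentions relatedness.
- A further instruction reads: "It is recommended to confirm the causal relationship of each non-serious or serious adverse event with the investigator, before updating database".

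Section 7.1 describes the trial as open-label and randomised. Section 6.2 makes safety and tolerability in each arm a secondary objective. The text of section 12.2 added after amendment 5.0 plans a comparison of VIT with VI "for all efficacy and safety endpoints".

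**The concern.** A relatedness condition at the point of recording makes the data depend on a judgement that the investigator forms knowing the treatment arm. VIT adds a third drug to which an event can be attributed, so the same event may be called related more readily in that arm. A difference in recorded rates could then arise with no difference in true rates, or a real difference could be masked.

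The comparison in section 12.2 would use these data. That section also says that the toxicity of the regimens will be weighed when deciding whether VIT merits further study, and that recruitment may be halted if severe toxicities significantly exceed 15%.

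The condition covers source documents as well as the eCRF. A non-serious clinical event left out at the site may therefore not be recoverable, and no later analysis plan could restore it.

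**Working it through.** The protocol has no figure of its own to reproduce on this point. The check is a comparison of texts, followed by an illustration of size.

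**Step 1: what each instruction implies for an event judged unrelated**

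| Type of data | Opening sentence of 11.2.2 | Other text | Result |
|---|---|---|---|
| Serious adverse event | Outside the recording rule | 11.2.2 list takes all of them; 11.2.3 counts death from any cause; 11.2.4 requires notification of any serious event from consent to 30 days after last treatment | Captured |
| Blood counts and chemistry | Not addressed as assays | 10.2.1 and 10.2.2 schedule them; the safety assessments section names them as a separate safety parameter | Captured |
| Non-serious clinical event | Outside the recording rule | 11.2.1 defines it as an adverse event; the 11.2.2 list has no relatedness filter | Contradictory |

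In the third row, the first item of the list says which grade to enter per cycle. It does not say whether unrelated events count, and it lacks the word that opens the serious-event item. It neither repeats nor revokes the opening condition. The causality assessment would be largely redundant if every recorded event were already judged related, so it points towards unfiltered recording. The text leaves the matter unsettled, and sites could reasonably differ.

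**Step 2: how attribution would carry into recorded rates**

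If the opening sentence is followed,

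recorded rate = true all-cause rate × probability that the event is judged related.

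All inputs here are assumptions except the allocation. Section 12.1 gives 1:1 randomisation and 120 patients in total, so about 60 per arm. True rates are set equal in the two arms. The last column is the chance that a pooled two-proportion normal test (two-sided 5%) finds a difference.

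| True rate, both arms | Attribution VI / VIT | Recorded VI / VIT | Spurious difference | Chance of a significant result |
|---|---|---|---|---|
| 20% | 50% / 75% | 10% / 15% | 5 points | 13% |
| 20% | 80% / 90% | 16% / 18% | 2 points | 6% |
| 40% | 80% / 90% | 32% / 36% | 4 points | 7% |
| 60% | 80% / 90% | 48% / 54% | 6 points | 10% |
| 20% | 60% / 90% | 12% / 18% | 6 points | 15% |
| 40% | 60% / 90% | 24% / 36% | 12 points | 30% |
| 60% | 60% / 90% | 36% / 54% | 18 points | 51% |
| 40% | 60% / 60% | 24% / 24% | 0 | no spurious difference |

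First row written out: 0.20 × 0.50 = 0.10 and 0.20 × 0.75 = 0.15. With 60 per arm that is 6 versus 9 patients.

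The last row shows that equal attribution creates no spurious difference between arms, but incidence is still understated: 40% is recorded as 24%. If all events were recorded whatever the attribution, equal true rates would give equal expected recorded rates.

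**The case against.** A reader might infer that adverse events are recorded only when judged related. The documents do not support that. Serious events are recorded and notified whatever their cause, and laboratory assays follow a schedule. Even for non-serious events the opening sentence does not contain the word only. The adverse event assessments in 10.2.1 to 10.2.3 carry no relatedness filter, and the causality item extends to study procedures, which presumes that events not caused by the drugs are recorded. All of this stands. It limits the point to non-serious clinical events and makes it an internal contradiction, not a demonstrated decision to discard unrelated events.

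A reader might also infer that the safety comparison is biased. That requires two things: that sites followed the opening sentence, and that attribution differed by arm. The protocol has no figure for the second. Both arms contain vincristine and irinotecan, and section 8.1 defines study medication as the combination with or without temozolomide, so diarrhoea or neurotoxicity can be attributed in either arm. Myelosuppression, which section 5.5 contrasts with diarrhoea as the other toxicity of the irinotecan-temozolomide pair, is measured by scheduled blood counts. With attribution of 80% versus 90%, the spurious differences are only 2 to 6 points. This also stands: bias is a risk, and may be small.

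Finally, the ancillary objective in 6.3 names response, progression-free survival and overall survival, not safety, and the primary endpoint is untouched. That is correct, but section 12.2 does plan the safety comparison.

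None of this removes the contradiction. The unfiltered list shows what may have been intended; it does not tell a site which sentence governs.

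**Conclusion.** The point holds in limited form. The opening sentence of 11.2.2 conflicts with the definition in 11.2.1 and with the reporting list and causality assessment in 11.2.2 itself. Whether unrelated non-serious clinical events were captured cannot be determined from the protocol. Where a site followed the opening sentence, incidence is under-recorded. If attribution also differed by arm, the VIT versus VI comparison of these events could be distorted in either direction.

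The size is unknown. Under the assumed attribution rates above, the spurious difference runs from 0 (equal attribution) to 18 points (60% versus 90%, true rate 60%). Serious adverse events, scheduled laboratory values and the primary endpoint are not affected. The wording should be corrected because it governs what data exist, and an analysis plan cannot repair that afterwards.

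**What to change.** Delete the relatedness condition from the opening sentence of 11.2.2, so that all adverse events in the stated grade range are recorded with causality as a variable, in line with 11.2.1 and the reporting list. State in section 12.2 that the main between-arm safety comparison uses all-cause adverse events, with related events secondary.

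For data already collected, first establish which instruction sites followed, for example from eCRF completion guidance and from whether non-serious events marked unrelated appear in the database. Where the restriction was applied, label the non-serious comparison as investigator-attributed and report all-cause serious adverse events and laboratory grades alongside it. It would be premature to set the non-serious events aside before that is known, since the eCRF list may have captured them all.

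The cost is more non-serious adverse event rows to enter in the eCRF, plus a one-off check of existing data. Summaries restricted to related events stay available.

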11.2.3. Serious adverse events – definition

A serious adverse event (SAE) includes, but is not necessarily restricted to, any event which:

- Results in death (whatever may be the cause)
- Is life-threatening
- Results in persistent or significant disability/incapacity
- Requires patient hospitalization or prolongation of existing hospitalization
- Is a congenital anomaly or birth defect
- Other events including cancer, over-dosage, pregnancy and any additional adverse experience or abnormal laboratory values occurring during the study period defined by the protocol as serious or which the investigator considers significant enough or that suggests a significant hazard, contraindication, side effect or precaution will be handled as a serious adverse event.

All deaths occurring while the patient is on study including deaths due to disease progression and deaths within 30 days of last administration of study drug should be notified as SAE.

11.2.4. Reporting of Serious of adverse events

A written agreement between the Coordinating Centre of each country and Sponsor should be obtained to clarify who is taking over the responsibility of informing competent authorities, ethics committees and investigators of this country to avoid double notification of safety information.

In the event of the occurrence of any SAE between signature of main informed consent form and the end of the 30-day follow up period after last treatment with study drug, irrespective of the treatment received by the subject, the Investigator is obliged to inform the Sponsor's designated Safety Desk immediately.

The investigator has to follow each SAE until its resolution and to transmit follow-up information as soon as available (detailed description and a final evaluation of the case, including copies of hospital reports, autopsy reports, or other relevant documents) to the Sponsor's Safety Desk.

The investigator has to answer to additional information requests by the Sponsor's Safety Desk or the monitor.

SAE notification to the Sponsor's Safety Desk by the Investigator is performed as follows:

	If SAE was NOT fatal nor life-threatening	If SAE was fatal or life-threatening	
		During business hours From Monday to Friday from 8:30 AM to 6:30 PM (French time), except from French bank holidays*	Outside business hours - Outside French bank holidays: From Monday to Friday from 6:30 PM to 8:30 AM (French time), on Saturdays and Sundays - At any time during French bank holidays*
Notification form	LONG SAE NOTIFICATION FORM (duly signed and dated)	LONG SAE NOTIFICATION FORM (duly signed and dated)	SHORT SAE NOTIFICATION FORM (duly signed and dated)
Instructions for transmission	Once completed, the form must be sent by e-mail to: [contact] (in case of any issue preventing the use of e-mails, the form may be sent by [contact])	Once completed, the form must be sent by e-mail to: [contact] (in case of any issue preventing the use of e-mails, the form may be sent by [contact]) AND The sponsor must be informed by [contact] (If no dedicated staff is available, the sponsor will give the investigator instructions to transmit the SAE to a hospital pharmacist.) If no sponsor staff answers the phone: The form must be sent by e-mail to: [contact] (in case of any issue preventing the use of e-mails, the form may be sent by [contact]) AND A hospital pharmacist must be warned by phone, via the central telephone desk of Centre Oscar Lambret: [name]	Once completed, the form must be sent by e-mail to: [contact] (in case of any issue preventing the use of e-mails, the form may be sent by [contact]) AND [contact] (in case of any issue preventing the use of e-mails, the form may be sent by [contact]) AND The on-duty intern must be informed by [contact]

* French bank holidays: January 1, Easter Monday, May 1, May 8, Ascension Day, Whit Monday, July 14, August 15, November 1, November 11, December 25

11.2.5. Pregnancies

In the event of a pregnancy occurring during the course of the study, the female subject still under study therapy must be withdrawn from the study medication immediately. The Sponsor must be notified without delay via the Safety desk (as described in section 11.2.4 above). The same applies to pregnancies occurring within 6 months after the last administration of study treatment. The subject must be followed during the entire course of the pregnancy and postpartum period. Parental and neonatal outcomes must be recorded even if they are completely normal and without AEs.

In case a male subject fathers a child during the course of the study, the subject can continue study treatment but the Sponsor must be notified without delay. The same applies to pregnancies occurring within 6 months after the last administration of study treatment. The

child's mother must be followed during the entire course of the pregnancy and postpartum period. Parental and neonatal outcomes must be recorded even if they are completely normal and without AEs.

11.2.6. *Sponsor's responsibilities*

- *Determination of expectedness/unexpectedness of Serious Adverse Reactions (SAR)*

A Serious Adverse Reaction (SAR) is a SAE related to study treatment. A SAR will be considered as expected when already mentioned in the safety reference document(s) of study treatment. Nevertheless, all expected adverse reaction which differ on intensity, evolution or frequency will be considered as a Suspected Unexpected Serious Adverse Reactions (SUSAR).

- *Recording of vigilance data and immediate reporting of Suspected Unexpected Serious Adverse Reactions (SUSAR)*

The sponsor will be responsible for the recording and updating of all vigilance data regarding the study.

The sponsor will also notify all Suspected Unexpected Serious Adverse Events to regulatory authorities (National Competent Authority and Ethic Committee) and inform all the investigators, in accordance with applicable laws and regulations.

Moreover, the sponsor transfers all relevant safety information to the Coordinating Centre of each country. He/she ensures that the responsible competent authorities, ethics committees and investigators participating within his/her country are informed of all SUSARs and all other relevant safety information in accordance with national legal requirements.

- *Periodic Safety Reports*

The Sponsor will prepare and submit appropriate periodic safety reports to regulatory authorities (National Competent Authority and Ethic Committee), in accordance with applicable laws, regulations and guidelines.

Periodic safety reports will be distributed via the Coordinating Investigators to responsible competent authorities and ethics committees in a timely manner.

12. STATISTICAL CONSIDERATIONS

12.1. Sample size

The primary endpoint of this clinical trial is response to treatment. The criteria for the evaluation of the primary endpoint is the objective response (success) rate.

Original study design (before amendment 4.0, in December 2015)

The maximum response rate for inefficacy is 20% (null hypothesis $H_0: p_0 \leq 0.20$). The minimum response rate for efficacy is 40% (alternative hypothesis $H_1: p_1 \geq 0.40$), for an expected difference of 20% ($p_1 - p_0$).

Using an Optimum 2 stage Simon design (with $\alpha=0.10$ and $\beta=0.10$), the first stage requires 17 eligible and evaluable patients in each arm. Decision rules with this design are applied to the VIT arm. In the first stage, if 3 patients or less among 17 patients in the VIT arm show a treatment success (17.6%), the trial should close prematurely and the experimental treatment be considered insufficiently active, that is to say with a success rate significantly less than 40%, which corresponds to a rejection of H_1 . If at least 4 patients among 17 patients in the VIT arm have a treatment

success, the second stage will continue to accrue 20 extra patients for a total of 37 patients in each arm. The same number of patients will be randomised to the VI arm which is used as the control arm.

At the end of the second stage, if 10 patients or less among 37 patients in the VIT arm have a treatment success, the treatment is considered insufficiently active, that is to say with a success rate significantly less than 40% (rejection of H1). If at least 11 patients among 37 patients show a treatment success, the treatment can be considered sufficiently active for further study in phase III. The success rate can be considered significantly greater than 20% (rejection of H0).

With this Optimum design, there is a 55% probability of early termination and the expected sample size under the null hypothesis is 26.02.

A total of 74 evaluable patients are required (37 per arm). Accounting for a 8% expected loss to follow-up rate (non evaluable), total accrual should reach **80** patients.

Patient recruitment will be interrupted between the two stages. Responses will be evaluated by central review once the first 17 evaluable patients of arms A and B have completed 2 cycles of treatment after which time a decision will be made to continue or not with the second stage. Inclusion interruption should last between 3 to 4 months.

Revised study design after amendment 4.0, in December 2015

IDMC reviewed the data analysis of the first 80 patients.

At that date, 80 patients (68 in the relapse status) had been enrolled with an annual accrual rate of 28 patients, which is higher than expected.

Based on the analysis, the IDMC considered that preliminary results indicate that more precision is needed, not only for the primary endpoint, but also for the secondary endpoints which will be used in planning the next phase III trial. They recommended that, in order to obtain a sufficient power to differentiate both arms and not to stop the European dynamic, the inclusion of a total of 120 patients (108 patients in the relapse status) in the VIT trial, should allow sufficient accuracy for choosing the standard arm: VI or VIT. The accrual of 40 extra patients should prolong the VIT trial one year.

The increase in the sample size is justified by the change in the statistical hypotheses since the IDMC recommended continuing the inclusion of only patients in relapse, refractory patients being no longer eligible for inclusion. Also, since the next trial will not be ready for another year, the extra patients in this trial should allow sufficient accuracy for choosing the standard arm in the next trial. The new design parameters are the following ($p_0=0.35$, $p_1=0.55$, $a=0.10$ and $b=0.10$) which lead to 47 evaluable patients. With 15% of lost follow-up (ineligible and non evaluable), 54 patients per arm should be included, for a **total of 108 randomized relapse patients**. Since 68 patients in relapse are already included, a total of **40 additional patients** in the relapse status should be included. With the new design parameters, if at least 22 patients among the 47 in the VIT arm show a treatment success, the treatment can be considered as sufficiently active. If 21 or less among 47 patients in the VIT arm have a treatment success, the treatment is considered insufficiently active.

Randomization 1:1 will be stratified for recurrent vs. refractory status and country for the first 80 patients. For the 40 additional patients in the relapse status, stratification by minimization will be performed for prior radiotherapy (yes vs no), country and recurrence (metastatic vs locoregional) according to the importance of these factors on the PFS curve.

12.2.

Statistical analyses

The main analysis will be performed on the intent to treat principle, considering all patients included in the study. Patients who withdraw from the study will be accounted for up until the time they withdraw from the study. Secondary analyses will be performed on the per protocol population, that is eligible, evaluable and treated patients. Safety analyses will be performed on all treated patients. Eligible patients are defined as patients who did not have a major violation of eligibility criteria (inclusion and exclusion criteria).

Treated patients are defined as patients who received at least one injection of the study treatment.

Evaluable patients for main objective (objective response at 2 cycles) are defined as patients who received at least 2 cycles of the study treatment and whose the tumor evaluation at 2 cycles was available.

The estimated difference in response rates between the two arms, will be presented with a 90% confidence interval. A Bayesian analysis of the final data will also be performed in which probabilities that one arm is better than the other will be given.

The risk / benefit ratio will be examined biannually by the IDMC on validated data. The sponsor may decide to temporarily halt recruitment to the trial if the rate of severe toxicities significantly exceeds 15%.

The decision rules for early termination are applied to the VIT arm as the VI arm is only used for controlling selection bias. However, at the end of the trial, if the VIT arm is considered sufficiently active, a phase III trial may be initiated. If the VIT arm is considered insufficiently active, this treatment strategy is rejected and other options should be considered. The cut points for acceptable and unacceptable response rates, obtained from the Optimum Simon design, will be used as guidelines for deciding whether VIT is worthy of further investigation; the response rate in the VI arm, the toxicity of the regimens and relevant external evidence will also be taken into consideration. Categorical variables will be presented as frequencies and percentages. Continuous variables will be presented as means (standard deviation), and medians (range). The treatment groups will be compared for demographic and initial disease characteristics using Fisher's exact test for categorical variables and the non-parametric Wilcoxon test for continuous variables.

Response rates will be estimated in each treatment group along with a 90% confidence interval. Survival rates will be estimated according to the Kaplan-Meier method. Median survival times will be presented along with a 95% confidence interval. Correlations will be evaluated with the Spearman correlation coefficient.

After amendment 5.0 in July 2018

A comparison between arms VIT vs VI will be performed to estimate the relative effect of VIT compared to VI, for all efficacy and safety endpoints. Objective response rates will be compared using Mantel-Haenszel Chi 2 test adjusted for confounding factors (histological subtype: alveolar, including pure or alveolar component vs non alveolar; and disease status at study entry: metastatic relapse/progression vs localised disease). OS and PFS curves will be compared using stratified logrank tests. Hazard ratios will be estimated using Cox models controlling for confounding factors. A future multi-arm multi-stage randomised phase II/III trial (FaR-RMS) plans comparing selected experimental arm(s) to control arm in the same setting. If the VI treatment is kept as a control arm and VIT as one of the experimental arms for the FaR-RMS trial, a joint analysis of both trials (VIT

and FaR-RMS) will be planned in order to provide efficacy results of VIT vs VI comparison (response rate, OS and PFS curves) on a larger sample of patients.

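### The extension is justified by power to tell VIT from VI, but the only sizing tests VIT against a fixed 35%, and its roughly 90% power does not carry over to the comparison of arms

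*Protocol*

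**What the plan says.** Section 12.1 (revised design after amendment 4.0) reports that the IDMC, having seen the first 80 patients, recommended "the inclusion of a total of 120 patients (108 patients in the relapse status"). The reason given is "in order to obtain a sufficient power to differentiate both arms", and the enlarged trial "should allow sufficient accuracy for choosing the standard arm: VI or VIT". The next paragraph repeats, in the protocol's own voice, that the extra patients should make the choice of standard arm for the next trial accurate enough.

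The sizing follows: null rate 0.35, target rate 0.55, alpha 0.10 and beta 0.10, giving 47 evaluable patients. The rule is that VIT counts as sufficiently active "if at least 22 patients among the 47 in the VIT arm show a treatment success". Accrual is then set: "With 15% of lost follow-up (ineligible and non evaluable), 54 patients per arm should be included", for a "total of 108 randomized relapse patients".

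Section 12.2 applies the decision rules to the VIT arm because "the VI arm is only used for controlling selection bias". It treats the cut points as guidelines and says the VI response rate, toxicity and external evidence will also be weighed. It plans a 90% confidence interval for the difference in response rates and a Bayesian analysis. Amendment 5.0 adds a Mantel-Haenszel test of response between the arms. Section 6.3 lists the relative effect of VIT as an ancillary estimation objective.

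**The concern.** The stated purpose of the 40 extra patients is comparative, while the calculation that produces their number has one arm. A one-arm test treats the reference rate as known exactly. A comparison with a randomised control must also carry the sampling error of the control arm, so the same number per arm gives much less power for the same 20-point gap. Nowhere does the protocol give a between-arm difference, significance level or power.

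The result is meant to inform the choice of standard arm for the next trial. Someone relying on section 12.1 could suppose that the comparison of arms is powered as well as the one-arm rule, and so give too much weight to an observed difference, or to its absence.

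**Working it through.** **Inputs from section 12.1.** Null rate 0.35, target rate 0.55, alpha = beta = 0.10, 47 evaluable patients, cut-off 22, 15% loss, 54 per arm, 108 relapse patients, 120 in total, 1:1 allocation.

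**1. Reproducing the plan's figures.** An exact search for the Simon optimal two-stage design with these parameters gives n = 47 (continue if more than 7 of 20 respond; final cut at more than 20 of 47; alpha 0.094, power 0.905). The rule as stated, read as a single-stage test, gives:

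- P(X ≥ 22 | n = 47, p = 0.35) = 0.063
- P(X ≥ 22 | n = 47, p = 0.55) = 0.899

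So 47 and the roughly 90% power both reproduce, for VIT against a fixed 35%. Accrual reproduces as 47 × 1.15 = 54.05, hence 54 per arm and 108 in total.

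**2. Power for VIT versus VI.** The protocol gives no between-arm effect or test level. Assumption: VI 35%, VIT 55%, the protocol's own two rates. With n per arm and mean rate 0.45 (normal approximation, pooled null variance):

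power = Φ{ [0.20·√n − z·√(2 × 0.45 × 0.55)] / √(0.35 × 0.65 + 0.55 × 0.45) } = Φ{ [0.20·√n − 0.7036·z] / 0.6892 }

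Example, n = 47, two-sided 5%: (1.3711 − 1.3789) / 0.6892 = −0.011, so power is 0.50.

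| Patients per arm | Two-sided 5% | Two-sided 10% | One-sided 10% |
|---|---|---|---|
| 47 (evaluable target) | 0.50 | 0.62 | 0.75 |
| 54 (all relapse patients) | 0.55 | 0.67 | 0.80 |
| 60 (all 120, intention to treat) | 0.60 | 0.72 | 0.83 |
| n per arm for 90% power | 128 | 105 | 80 |

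The last row is n = (0.7036·z + 1.2816 × 0.6892)² / 0.04, rounded up.

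**3. Precision of the difference.** Half-width of the 90% interval = 1.645 × √[(0.2275 + 0.2475)/n]. This is 0.165 at n = 47, 0.154 at n = 54 and 0.146 at n = 60, so about 15 to 17 points.

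**4. Loss allowance.** If 15% of those randomised are lost, 54 × 0.85 = 45.9, about 46 evaluable. Keeping 47 would need 47/0.85 = 55.3, i.e. 56 per arm and 112 in total. The loss that leaves exactly 47 of 54 is 1 − 47/54 = 13.0%. With 46 evaluable:

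- cut-off at least 22: power 0.870
- cut-off at least 21: alpha 0.089, power 0.922

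**The case against.** Four points count on the other side.

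- The power phrase sits in a sentence reporting the IDMC's recommendation, and the protocol goes on to justify the number by changed one-arm hypotheses. A careful reader can see that the 0.10/0.10 belongs to the VIT rule. This stands: a reader might infer that the protocol claims 90% power for VIT versus VI, but it attaches no figure to that comparison. Attribution does not remove the mismatch, because the claim about choosing the standard arm is repeated in the protocol's own voice and no between-arm calculation supports either statement.
- Sections 6.3 and 12.2 already frame VIT versus VI mainly as estimation. This also stands. One might fear that a non-significant difference will be declared equivalence, but no section says so. The correction brings section 12.1 into line with the rest of the protocol.
- Choosing a standard arm need not mean a significance test. At 35% versus 55%, exact enumeration gives a 97% chance that VIT has more responders with 47 per arm, and 98% with 54. At 35% versus 45% the chance is 81% and 83%. That is a legitimate design property, but it is not power and the protocol does not state it.
- The loss arithmetic amounts to about one patient. Agreed. One might infer that 47 is wrong or that the primary decision is compromised. Neither follows: 47 reproduces, section 12.2 makes the cut points guidelines, and a cut-off of 21 in 46 keeps both error rates within 10%.

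**Conclusion.** The point holds as a mismatch between a stated property and the calculation offered for it. The roughly 90% power belongs to VIT against a fixed 35%. For VIT versus VI at an assumed 35% versus 55%, power runs from 0.50 (47 per arm, two-sided 5%) to 0.83 (60 per arm, one-sided 10%), so even the most favourable combination falls short of 90%. These figures rest on the assumed rates and on an unstratified comparison; a smaller true difference would lower them.

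This does not show that the one-arm decision rule is invalid or that the trial must be larger. The loss allowance is a minor remark: 54 per arm corresponds to 13% loss, and the stated 15% leaves about 46 evaluable patients, for whom the protocol gives no cut-off.

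**What to change.** In section 12.1:

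1. State that the 90% power applies to VIT tested against a fixed response rate of 35%.
2. Replace the wording about power to differentiate the arms with the between-arm power at a named difference and test level (the table above can serve), together with the expected 90% interval half-width of about 15 to 17 points. Describe the comparison as estimation, as sections 6.3 and 12.2 already do. If selection of the better arm is what is meant, say so and give the probability of correct selection.
3. As a minor correction, either state that 54 per arm allows for 13% loss, or keep 15% and give the cut-off for the evaluable number reached (for 46, at least 21: alpha 0.089, power 0.922).

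The cost is a text change only. No patients are added; the stated properties become less favourable but match what the design delivers.
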